10.2 Duration of Response

10.2.1. Duration of overall response:

The duration of overall response is measured from the time measurement criteria are met for symptomatic, splenic or erythropoietic response (whichever is first recorded) until the first date that recurrent or progressive disease is objectively documented (taking as reference for progressive disease the smallest measurements recorded since the treatment started)

10.2.2. Duration of stable disease:

Stable disease is measured from the start of the treatment until the criteria for progression are met, taking as reference the smallest measurements recorded since the treatment started.

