6.3. Treatment Phase

6.3.1. Cycle 1, Day 1 (D0) Testing and Procedures:

- 6.3.1.1. 6.3.1.1. Pre-dose evaluation:History and Physical Exam
- 6.3.1.2. Record palpated Spleen size
- 6.3.1.3. Laboratory Testing
 - CBC
 - CMP
 - Uric Acid
 - Phosphorus
 - LDH
- 6.3.1.4. Establish and Record Baseline Hemoglobin: Baseline Hemoglobin is defined as the median hemoglobin within 28 days of Cycle 1, Day 1 (D0).
- 6.3.1.5. EKG (QTc) in the event of a dose increase
- 6.3.1.6. Complete MPN-SAF-TSS Myeloproliferative symptom assessment form total symptom score)³³ (Appendix A)
- 6.3.1.7. Record baseline co-morbidities and pre-existing symptoms.

- 6.3.1.2. Dispense study drug (vactosertib 50 mg tabs, #130) for cycle from research pharmacy and deliver to eligible subject during clinic visit.
- 6.3.1.3. Starting dose for Tier 1 is DL1. Subject will receive the one dose of vactosertib (DL1) under supervision of treating physician or research study nurse.
- 6.3.1.4. Research blood sample (20mL) will be collected either with SOC labs (if they are on a stable dose of vactosertib) or one hour after vactosertib dose (if dose of vactosertib is modified).
- 6.3.1.5. Subject will return for Follow-up Testing and Procedures (section 6.3.2) in 7 (\pm 2) days after first dose of vactosertib.

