10.1.3 Erythropoietic Response

Defined by any of the following:

- HGB increase of 1.5g/dL compared to baseline HGB;
- Reduction in PRBC transfusion rate to $\leq 50\%$ of pre-treatment transfusion rate; or
- Reduction in PRBC transfusions by ≥ 4 Units over an 8-week period.

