12.2.2 Composite response/ Toxicity measure

Responding subjects will have met *Criteria for Clinical Benefit* ([section 9.1](#)) for at least 8 weeks. This will ensure that a stable vactosertib dosing schedule can be achieved. Responding subjects will not experience dose limiting toxicity (see *Definition of Dose Limiting Toxicity*). Only subjects meeting all criteria will be considered responders.

Table 5: Composite Response & Toxicity Endpoint

Adequate Response	Meets Criteria for Clinical Benefit
Stable Response	Meets Criteria for Clinical Benefit to vactosertib for \geq 8 weeks
Tolerable	No Dose Limiting Toxicity Experienced

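### Section 10.2.1 measures progression from the smallest value, which for hemoglobin is the worst value, so a lost hemoglobin response can be reported as ongoing

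*Combined protocol and SAP*

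**What the plan says.** All references are to the combined protocol and SAP.

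- **Start of the clock (10.2.1).** Duration of overall response is "measured from the time measurement criteria are met for symptomatic, splenic or erythropoietic response (whichever is first recorded"), so a subject who responds on anemia alone falls under this rule.
- **End of the clock (10.2.1).** It runs "until the first date that recurrent or progressive disease is objectively documented", with the qualifier "taking as reference for progressive disease the smallest measurements recorded since the treatment started". There are two triggers, and the qualifier is attached only to the second, progressive disease.
- **Erythropoietic response (10.1.3).** Any one of three criteria is enough: "HGB increase of 1.5g/dL compared to baseline HGB"; "Reduction in PRBC transfusion rate to" half of the pre-treatment rate or less; or at least 4 fewer units over 8 weeks.
- **Baseline (6.3.1.4).** "Baseline Hemoglobin is defined as the median hemoglobin within 28 days of Cycle 1, Day 1 (D0").
- **Related definitions.** In 10.2.2, "Stable disease is measured from the start of the treatment until the criteria for progression are met", again with the smallest measurements as reference. Section 10.3 times PFS to progression without defining it.
- **Durability in the composite (12.2.2, Table 5).** This is a separate rule: "Meets Criteria for Clinical Benefit to vactosertib for" at least 8 weeks.

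The plan does not define *recurrent*, does not define progression in terms of hemoglobin, and has no loss-of-response rule.

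**The concern.** The reference to the smallest measurement is the usual rule for lesions, where the smallest value is the best one reached and regrowth from it is failure. Hemoglobin moves the other way. A response that starts as a rise from baseline is here ended, on the progression trigger, by comparison with the on-treatment nadir. A subject can give back the whole rise and still sit at or above that nadir.

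Anemia is the condition the trial sets out to treat, so hemoglobin responders are the subjects whose durations readers will look at first. If the progression trigger is applied literally, those durations are too long. If one analyst treats returning anemia as recurrence and another does not, the same data give two answers, and the choice could be made after the results are known.

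**Working it through.** No figure in the plan rests on 10.2.1, so there is none to reproduce. The check is of direction, followed by two illustrations. All hemoglobin and transfusion values below are assumed; only the criteria come from the plan.

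**1. Direction, by component**

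| Measure (source) | Better when | Smallest value is | Worsening from the smallest value detects loss? |
|---|---|---|---|
| Symptom score (10.1.1) | lower | best | yes |
| Spleen size (10.1.2) | lower | best | yes |
| Transfusions (10.1.3) | lower | best | yes |
| Hemoglobin (10.1.3) | higher | worst | no |

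Transfusion example: 6 units per 8 weeks falls to 2. Both transfusion criteria are met (half of 6 is 3, and 6 − 2 = 4). A return to 6 is 6/2 = 3 times the smallest value, which the rule can detect.

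**2. Why hemoglobin fails**

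Let H(t) be hemoglobin at visit t and m(t) the smallest value from the start of treatment to t. By construction H(t) − m(t) ≥ 0 at every visit, because each new low becomes the reference. A fall therefore never goes below the reference; only a rise moves away from it. A kinder reading takes the smallest value before the current visit as reference. A fall below the old nadir could then count, but only after the entire gain had gone, and the plan states no size of worsening.

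**3. First illustration**

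Baseline 8.0 g/dL; nadir 7.4 at week 2; 9.5 or more at every assessment from week 8 until just before week 20; 8.0 at week 20, no transfusion.

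- Response threshold: 8.0 + 1.5 = 9.5.
- Duration by the 10.1.3 criterion: 20 − 8 = 12 weeks.
- Distance from the 10.2.1 reference at week 20: 8.0 − 7.4 = +0.6, so no progression is recorded.
- Even on the kinder reading, hemoglobin would have to fall below 7.4, which is 9.5 − 7.4 = 2.1 g/dL under the response threshold.

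**4. Second illustration, with gradual loss** (baseline 8.0, no transfusion)

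| Week | HGB | Change from baseline | Criterion met | Above smallest so far |
|---|---|---|---|---|
| 0 | 8.0 | 0.0 | no | 0.0 |
| 2 | 7.6 | −0.4 | no | 0.0 |
| 4 | 8.2 | +0.2 | no | 0.6 |
| 6 | 9.0 | +1.0 | no | 1.4 |
| 8 | 9.6 | +1.6 | yes | 2.0 |
| 10 | 9.8 | +1.8 | yes | 2.2 |
| 12 | 9.7 | +1.7 | yes | 2.1 |
| 14 | 9.0 | +1.0 | no | 1.4 |
| 16 | 8.4 | +0.4 | no | 0.8 |
| 18 | 8.0 | 0.0 | no | 0.4 |
| 20 | 7.8 | −0.2 | no | 0.2 |
| 22 | 7.7 | −0.3 | no | 0.1 |

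By the 10.1.3 criterion the duration is 14 − 8 = 6 weeks. On the progression trigger the response is still running at week 22, that is 22 − 8 = 14 weeks or more, with hemoglobin 0.3 below baseline.

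**5. Does it reach the go/no-go decision?**

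Table 4 continues with at least 1 responder of 12 and succeeds with at least 4 of 37, for response rates of 0.05 against 0.20. The probability of success is the sum over x = 1 to 12 of P(X = x; 12, p) × P(Y ≥ 4 − x; 25, p). This gives 0.0935 at p = 0.05 and 0.902 at p = 0.20, within the stated 10% limits for both errors. Responders are counted by Table 5, which carries its own 8-week requirement, so 10.2.1 does not enter.

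**The case against.** A reader might infer that the plan counts lost anemia responses as ongoing, full stop. The text does not support that, for two reasons.

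- The smallest-value reference qualifies progressive disease only. *Recurrent* disease is a second way to end a response, and hemoglobin back at baseline can fairly be read as recurrence. This stands: miscounting follows from the progression trigger taken literally and is not certain. It does not rescue the rule, because the plan never says what recurrence is for any component.
- Two of the three erythropoietic criteria are falls in transfusion, and there the rule runs the right way. This also stands. If the subject in the first illustration had been transfusion-free and restarted transfusion at week 20, that could register as a rise from the smallest count. Hence the illustration excludes transfusion.

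A reader might also infer that the 8-week composite or the Simon decision is compromised. Neither uses 10.2.1.

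It can further be said that the IWG-MRT/ELN criteria fill the gap. Section 6.3.5.12 has them recorded at end of tier, and 6.3.7 uses them to judge stable disease for continued treatment. But 10.2.1 does not refer to them and states its own reference.

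Finally, duration of response is absent from the objectives, the endpoint list in section 1 and the analyses in 12.4. That is correct and limits the importance. It does not make the definition right, and section 10.2 gives no reason to define durations unless they are to be reported.

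**Conclusion.** Wrong as written, of low to moderate importance. For responses that rest on hemoglobin, the progression reference in 10.2.1 is the worst value on treatment, so losing the gain does not register as progression. Such a response can be carried as ongoing unless *recurrent* is taken to cover the loss.

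The effect is on reported durations of response only. Its size in the trial cannot be derived from the documents: it depends on how many subjects respond on hemoglobin alone, how many lose that response without resuming transfusion, and how *recurrent* is applied. The illustrations (12 weeks against still ongoing at week 20; 6 weeks against 14 or more) show the mechanism under assumed values and are not estimates. Durations based on transfusions, spleen or symptoms are not affected by the direction error, though they share the undefined terms.

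**What to change.** Rewrite 10.2.1 as follows.

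- End each component's response at the first date its own 10.1 criterion is no longer met. Judge hemoglobin against baseline. Assess both transfusion criteria (the 50% rate and the 4-unit reduction) over a stated 8-week window, which matches the 8-week history taken at screening under 6.2.2.10.
- State whether loss must be confirmed at the next visit, and which of the two dates then counts.
- State that overall response ends when no component remains met, or at progression or death.
- Keep the smallest-value reference only for measures where smaller is better.
- Define *recurrent* and *progressive* for each component, and align 10.2.2 and 10.3 with those definitions.

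**Cost.** Wording only. Hemoglobin, interval transfusions, palpated spleen size and symptom score are already collected at follow-up visits under 6.3.2. Reported durations will be shorter. Without a confirmation rule, one noisy hemoglobin value could end a response and bias durations the other way. With one, dating is limited by visit spacing, which 7.7.1 extends to about 4 weeks on a maintained dose. The change is to an analysis definition and should be settled before durations are analyzed.

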10.3 Progression-Free Survival

PFS is defined as the duration of time from start of treatment to time of progression.

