- To identify common toxicities of vactosertib in patients with Ph-neg MPNs.

Exploratory Objectives:

To assess the stem cell directed effect of vactosertib by quantifying the VAF of MPN driver mutations in stem, progenitor and mature cell populations isolated from PB or BM samples before and after treatment with vactosertib.

Endpoints:

Primary Endpoints: (Safety and Efficacy)

- Tier 1 (Safety endpoints):
 - Define the safest, minimally effective starting DL for Tier 2 ([section 5.3.5.1](#)).
 - Identify DLTs and, possibly the MTD of vactosertib in patients with MPN
- Tier 2 Efficacy endpoints ([section 9.1](#)):
 - Erythropoietic response as defined by the IWG-MRT criteria
 - Clinical response in symptoms as defined by IWG criteria.
 - Splenic response as defined by IWG criteria.^{2,3}
- Tier 2 Safety endpoints: Identify DLT and, possibly MTD

Secondary Endpoints:

- Histologic response defined by any reduction in grade of bone marrow fibrosis by histopathologic assessment at 16 weeks.
- Molecular response defined by a decrease in VAF of MPN-driver mutations (eg. JAK2, CALR, and MPL allelic ratio) in blood and/or bone marrow cells.
- Pharmacodynamic Response defined as any of the following:
 - Reduced immunohistochemical staining for SMAD2/3 phosphorylation in bone marrow biopsy sections (*See Figure 1*).
 - Reduced mean fluorescence intensity (MFI) of SMAD2/3 phosphorylation staining in peripheral blood and/or bone marrow HSPCs or mature progeny as assessed by flow cytometry (*See Figure 2*).
- The incidence of hematologic toxicities, infections, disease progression, thrombosis events, and the probability of overall and progression free survival, will be monitored.

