10.4. Other Response Parameters

10.4.1. Molecular response: measured by change in blood (and/or marrow) allelic ratio of MPN driver mutations (JAK2, CALR or MPL).

10.4.2 Histologic response: measured by change in bone marrow biopsy cellularity and fibrosis grade.

10.4.3 SMAD2/3 phosphorylation: Measured in peripheral blood and/or bone marrow hematopoietic cells.

11. Data Reporting / Regulatory Considerations

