12.4.2 Analysis of Secondary Endpoints

Clinical response to vactosertib will be assessed using the *Criteria for Clinical Benefit* outlined above as a composite endpoint. Patients achieving any of these criterial will be considered to have achieved clinical benefit. This endpoint will be used to define a preliminary estimate of the potential efficacy of vactosertib in the study population. Complete enrollment to both tiers (37 total) will allow us to confidently identify a *Clinical Benefit* response rate of more than 30%. This estimate has a significance of ≤ 0.1 and a power of 0.8 and is based upon a reported clinical improvement rate of $\leq 10\%$ (almost

entirely due to symptomatic response) in similar patient populations with best available therapy^{34,35}. Reported rates of splenic and/or erythropoietic responses to best available therapy are $\leq 3\%$. The 37 subjects enrolled on this study will allow Splenic Response and Erythropoietic Response rates of at least 20% to be individually tested with a power of 80% and a significance of $< 0.1\%$. If after complete accrual of 37 subjects, more than 11 patients meet criteria for Composite Response, or more than 7 patients meet criteria for Splenic or Erythropoietic Response, vactosertib will be considered to have sufficient efficacy for definitive testing in a randomized study.

The secondary endpoints of erythropoietic (HGB and RBC transfusion), symptomatic, and splenic responses will be directly tested as described in the preceding section. While limited by the small sample size, additional endpoints will be assessed including molecular (MPN driver variant allele frequency), pharmacodynamic (SMAD2/3 phosphorylation in bone marrow and/or blood CD34+ hematopoietic stem and progenitor cells), and histologic (bone marrow cellularity and fibrosis score) responses. The incidence of hematologic toxicities, infections, disease progression, thrombosis events, and the probability of overall and progression free survival, will be monitored. Secondary endpoints will be reported using descriptive statistics but no formal hypothesis testing will be performed.

Other secondary endpoints will be reported using descriptive statistics but no formal hypothesis testing will be performed. The following endpoints will be analyzed:

12.4.2.1 Histologic response defined by any reduction in grade of bone marrow fibrosis by histopathologic assessment at 16 weeks.

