12.4.2.2 Molecular response defined by a decrease in allelic ratio of MPN-driver mutations (eg. JAK2, CALR, and MPL allelic ratio) in blood and/or bone marrow cells.

12.4.2.3 Pharmacodynamic Response defined as any of the following:

- Reduced immunohistochemical staining for SMAD2/3 phosphorylation in bone marrow biopsy sections (See Figure 1).
- Reduced mean fluorescence intensity of SMAD2/3 phosphorylation staining in peripheral blood hematopoietic stem and progenitor cells (HSPCs) or mature progeny as assessed by flow cytometry (See Figure 2).
- Reduced mean fluorescence intensity of SMAD2/3 phosphorylation staining in bone marrow hematopoietic stem and progenitor cells (HSPCs) or mature progeny as assessed by flow cytometry.

12.4.2.4 ToxicityThe incidence of hematologic toxicities, infections, disease progression, thrombosis events, and the probability of overall and progression free survival, will be monitored.

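### Section 10.3 defines PFS with no death event and no censoring rule, so it is time to progression under a PFS label; secondarily, molecular and pharmacodynamic response count a decrease of any size

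*Combined protocol and SAP*

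**What the plan says.** **PFS.** Section 10.3 is one sentence: "PFS is defined as the duration of time from start of treatment to time of progression". The secondary endpoints in the Protocol Summary, and again section 12.4.2, state that "the probability of overall and progression free survival, will be monitored". Section 10.2.1 runs the duration of overall response "until the first date that recurrent or progressive disease is objectively documented" and does not mention death either. None of these sections gives a censoring rule or an estimator.

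**Follow-up.** Section 7.10 follows patients for 6 months after removal from study, or until death if that is sooner. The Protocol Summary (Study Duration) gives 2 months for patients who come off study and 12 months for those who complete it.

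**Molecular and pharmacodynamic response.** Section 10.4.1 treats molecular response as a quantity, "measured by change in blood (and/or marrow) allelic ratio of MPN driver mutations (JAK2, CALR or MPL". Section 12.4.2.2 makes it a yes/no outcome: "Molecular response defined by a decrease in allelic ratio of MPN-driver mutations", in blood and/or marrow. Section 12.4.2.3 has "Pharmacodynamic Response defined as any of the following", followed by three bullets that each require only a reduction. The blood flow-cytometry bullet accepts "peripheral blood hematopoietic stem and progenitor cells (HSPCs) or mature progeny as assessed by flow cytometry". Neither definition sets a minimum size or a time point.

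**Status.** Section 12.4.2 says "Secondary endpoints will be reported using descriptive statistics but no formal hypothesis testing will be performed".

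**The concern.** An endpoint whose only event is progression is time to progression. PFS also counts death. In a population with advanced disease some patients may die before progression is documented, and the plan leaves the analyst to decide after the fact whether to count, censor or otherwise handle them. If they are censored or treated as a competing risk, the figure labelled PFS will look as good as or better than true PFS, and readers will compare it with PFS from studies that count death.

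The secondary matter is interpretability. The secondary objective is to show on-target activity. If any fall in a noisy readout counts as a response, an inert drug would also give a high response count, so the count says little about activity.

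**Working it through.** **Inputs from the documents.** N = 37 (section 12.2); progression as the only PFS event (section 10.3); response rules (sections 12.4.2.2 and 12.4.2.3). The documents state no progression rate, death rate, expected PFS or estimator.

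**Assumptions for illustration.** k = 4 to 12 progressions, d = 1 or 3 deaths without progression, no other censoring, Kaplan-Meier estimation.

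**Step 1. The plan's own figures.** There is no PFS figure to reproduce. The section 12.1 rule (at least 1 responder in 12, then at least 4 in 37) does reproduce. The chance of passing is the sum over x = 1 to 12 of P(X = x in 12) × P(at least 4 − x in 25). It is 0.0935 at a 5% response rate and 0.902 at 20%, in line with the stated error limits of 10%. Only composite-responder counts enter; PFS does not.

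**Step 2. Deaths censored versus counted, at the end of the curve.**
- Death counted as an event: (37 − k − d)/37.
- Death censored, all deaths before the first progression (smallest gap): (37 − d − k)/(37 − d).
- Death censored, all deaths after the last progression (largest gap): (37 − k)/37, a gap of d/37.
- Death as a competing risk: 1 − k/37, again a gap of d/37.

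| d | k | Counted | Censored, deaths first | Censored, deaths last | Gap (points) |
|---|---|---|---|---|---|
| 1 | 4 | 32/37 = 86.5% | 32/36 = 88.9% | 33/37 = 89.2% | 2.4 to 2.7 |
| 1 | 12 | 24/37 = 64.9% | 24/36 = 66.7% | 25/37 = 67.6% | 1.8 to 2.7 |
| 3 | 4 | 30/37 = 81.1% | 30/34 = 88.2% | 33/37 = 89.2% | 7.2 to 8.1 |
| 3 | 12 | 22/37 = 59.5% | 22/34 = 64.7% | 25/37 = 67.6% | 5.2 to 8.1 |

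Over k = 4 to 12 the gap is 1.8 to 2.7 points for one death and 5.2 to 8.1 for three. With d = 0 it is zero.

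**Step 3. Response from noise alone.** Assume a continuous readout, no true change, symmetric error and one time point. Each readout falls with probability 0.5. If any one of m independent readouts may qualify, the chance is 1 − 0.5^m: 50% for m = 1, 75% for m = 2 (blood and marrow, molecular) and 87.5% for m = 3 (the three pharmacodynamic bullets). If the readouts are perfectly correlated it stays at 50%. So 50% is the floor for an evaluable patient.

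**Step 4. Precision of the alternative.** The 95% CI half-width for a mean paired change, in SD units, is t(0.975, n − 1)/√n: 0.33 for 37 pairs, 0.37 for 30, 0.47 for 20 and 0.64 for 12.

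**Step 5. A caution on the repair.** Suppose every death in 6 months of follow-up counts while survivors are censored at their last assessment. PFS can then err low. A simulation of 400,000 patients assumed progression at 0.3 per year, death at 0.05 to 0.2 per year, 20 to 60% leaving uniformly between months 1 and 6, and the rest last assessed at month 6. The largest gap in 6-month PFS was 77.9% true against 75.1%, or 75.9% if deaths count only within 8 weeks of the last assessment. That is about 3 and 2 points.

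**The case against.** **Weight.** PFS is descriptive, overall survival is listed beside it, and no threshold or comparator uses it. A death that results from an adverse event is a DLT (section 13.1.1), so that patient cannot be a composite responder (section 12.2.2). All this stands. A reader might infer that the trial's decision or error rates are compromised; step 1 shows that they are not.

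**Size.** The gaps rest on assumed events. With independent exponential times and an assumed 12-month progression risk of 30%, the gap would be 0.70 × 0.05 = 3.5 points at a 12-month death risk of 5%, and 0.70 × 0.30 = 21 points at 30%. Neither range comes from the documents. Sampling error is larger than the one-death gap: 1.96 × √(p(1 − p)/37) is about 10 points at p = 4/37 and 15 at p = 12/37. Three deaths also presuppose that accrual continues, since one grade 5 DLT within 12 weeks suspends it (sections 8.1.1 and 15); later deaths or a re-opening would be needed. These points limit the size but do not supply the missing event. A reader might also infer that the reported figure can never be compared with true PFS. If no such death occurs, the two coincide.

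**Noise rate.** Because the flow bullets admit stem and progenitor cells or mature progeny, a reader might count five pharmacodynamic readouts and infer a rate above 87.5%. The documents do not support that as a headline. Section 12.4.2 names CD34+ cells as the pharmacodynamic population, and cell types from one tube are unlikely to be independent.

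**Sampling.** A reader might take from section 6.3.2.4 that a one-hour post-dose pSMAD sample already exists on Day 1 of every cycle. Section 9.1.1.1 lists pSMAD blood only at Screening, End of Tier and new dose levels. Section 6.3.1.4 ties the one-hour draw to a dose modification, and the Tier 2 schedule table does not confirm the Day 1 draws.

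**Progression itself.** Section 6.3.5.12 refers to response criteria for MF, PV and ET, while section 4.2 also admits MDS/MPN and MPN-U. That is a fair separate gap, which adding death to section 10.3 does not close.

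**Conclusion.** The point holds, at minor to moderate severity. Followed as written, section 10.3 yields time to progression under a PFS label, and section 10.2.1 has the same silence on death in response. The direction is clear where deaths without progression are censored or treated as a competing risk: the reported figure equals or exceeds true PFS. The size cannot be known from the documents; the gaps in step 2 depend on the assumed events, Kaplan-Meier estimation and no other censoring.

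The secondary point also holds in limited form. The 50% floor applies per evaluable patient with a continuous readout and symmetric noise; 75% and 87.5% need independence as well. That any size of fall counts is inferred from the absence of a threshold, since the text says only that there is a decrease or reduction.

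**What to change.** - **Section 10.3:** define PFS as the time from start of treatment to first documented progression or death from any cause, whichever comes first, otherwise censored at the last disease assessment. State how deaths long after the last assessment are handled (step 5 shows why). Alternatively, relabel the endpoint time to progression.
- **Section 10.2.1:** state whether death in response ends the response or is censored.
- **Follow-up:** reconcile section 7.10 with the Protocol Summary, because the length of follow-up governs which deaths are seen.
- **Sections 12.4.2.2 and 12.4.2.3:** report the paired change from Screening with a 95% CI, in line with section 10.4.1, and label any count as any decrease. Use end of Cycle 4 for marrow and for VAF blood. Restrict VAF to patients with a tracked driver mutation at Screening, which section 4.2 does not require, and give that number.
- **pSMAD blood:** use a draw that section 9.1.1.1 lists, such as End of Tier, in the CD34+ population named in section 12.4.2. End of Tier falls after Cycle 4 in Tier 1 and after Cycle 6 in Tier 2, so report it by tier. Reconcile the research-blood timing in sections 6.3.1.4, 6.3.2.4 and 9.1.1.1 and the schedule tables.

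**Cost.** Wording and a routine paired analysis on draws the plan already lists, with no extra patients or visits. Reported PFS may be lower. Precision is 0.33 SD only with all 37 pairs; early removal, dry taps and patients without a tracked mutation will widen the interval as in step 4.
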